#### Extension phase

The extension phase will allow device access to all participants taking part in the study and will allow safety data to be collected over a longer period of time. The effects noted during this period are not of primary interest and the approach to analysing extension phase data will be largely exploratory.

We will describe the patterns in primary and secondary outcomes from 6 months to 12 months in Group A (receiving the intervention at both time points) and compare the 6-month post-intervention effect size in Group B to that observed in Group A during the primary study phase.

Primary and secondary outcome scores, paired differences, and their 95% confidence intervals will be presented.

9.2 The number of participants planned to be enrolled (if possible, include number at each site). Document the reason for choice of sample size, including reflections on (or calculations of) the power of the trial and clinical justification.

The power calculation is for a parallel study design with two groups of equal size.

The power calculation is for a parallel study design with two groups of equal size. Based on information in the WA population-based database and current data (de Bock et al, accepted JDST 2018), we expect a between group difference of 1.5% in HbA1c at 6 months with a SD of 1.7% for both groups. With alpha set at 0.05, 22 subjects would be required in each group to have 80% power to detect a difference of 1.5%. It is assumed the total dropout rate will be up to 15%, so we plan to recruit 50 subjects in total.

- 9.3 The level of significance to be used. P-values <.05 will be considered statistically significant and 2-sided P-values will be reported.
- 9.4 Procedures for reporting any deviation(s) from the original statistical plan (any deviation(s) from the original statistical plan should be described and justified in the protocol and/or in the final report, as appropriate).
   Any deviations to the original statistical plan will be reported to relevant ethics committees, governance committees, the Australia New Zealand Clinical Trial Register (ANZCTR), the DSMB and the manuscript.
- 9.5 The selection of participants to be included in the analyses (e.g. all randomised participants, all dosed participants, all eligible participants, or all evaluable participants).

The primary analysis will take a modified intention-to-treat approach, with all randomised participants who attended at least one visit following randomisation being included in the analysis. A secondary analysis using a 'per-protocol' sample (defined as participants with over 70% adherence to pump and sensor) will also be conducted.

9.6 Information on how data will be managed, including coding for computer analysis and data handling (collection, storage, maintenance, security and archiving). Include details regarding these processes if the data is sent off-site (e.g. encryption). *Clinical trial records should be retained for a minimum of 15 years from the completion of the trial.* 

All data will be anonymised and will not be able to be linked back to any individual participant. Data will be stored on secure servers and electronic device capture systems with secure access for study staff only and all data will be stored in an anonymised form that cannot be linked back to the original participant. All data will be stored for 25 years in line with GCP requirements on secure servers. Hard copies of patient notes will be stored in secure filing cabinets at each site and archived in secure facilities' at the end of the trial.

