#### VISIT 3 (4-6 hours)

This visit is the randomisation visit, and allocation is dependent on the stratifications detailed in Section 4.3.

The following data will be collected prior to randomisation:

- 1. Diabetes clinical
  - a. HbA1c
  - b. Total daily dose of insulin (mean of previous 7 days)
  - c. Severe hypoglycaemia in the run-in period
  - d. Diabetic ketoacidosis in the run-in period
  - e. Admissions in the run-in period
  - f. Pump upload
  - g. Sensor data in the 2 weeks prior to the study (in participants on CGM)
- 2. Diabetes education/review
  - a. Diabetes education: Diabetes educator session (2 to 4 hrs) as refresher to re-educate and optimise standard diabetes management
  - b. Carbohydrate Counting: Dietician review (1 to 2 hours)
     The duration of the session is variable according to the prior knowledge of the participant.
- 3. Retinal photographs, will be collected and retained for centralised assessment
- 4. INSPIRE questionnaire (baseline for participants randomised to AHCL)
- 5. Medtronic AHCL System Background Patient Questionnaire (optional)

6. Biomarkers

A detailed description of sample preparation for biomarkers is found in appendix

- 12mL of blood and 50mL of urine will be collected in fasting state
- a. Cell Adhesion Molecules (CAM)S
- b. Soluble vascular cell adhesion molecules sVCAM
- c. Soluble intercellular adhesion molecules sICAM
- d. s-e Selectin
- e. Oxidized Low density lipoprotein
- f. Myeloperoxidase.
- g. MicroRNA signatures for arterial, renal and retinal complications
- h. Telomerase
- i. DNA methylation/acetylation
- j. Glycomark
- k. Isoprostanes and proteomics
- I. Clotting profile

VISIT 4 (participants randomised to AHCL arm)

CSII to AHCL: Participant 780G, CGM education and AHCL training.

Visit 4A: Pump training (2 hours)

Participants will be trained on how to use the Medtronic 780G insulin pump. Participants will be provided with Roche Accu-Chek®glucometer along with the glucose strips for the study.

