#### Visit 4C: Commencement of AHCL (1 hour)

Once CGM data has been established for a minimum of 3 to 7 days, participant returns for face-toface instruction on AHCL use and initiation of Automode. During this visit, the sensor will be replaced to demonstrate sensor warm up and AHCL initiation, and provide an opportunity for those unfamiliar with CGM use to practice a sensor change with supervision. Upon AHCL initiation, participants will be instructed to avoid excessive exercise for 48hrs while the algorithm adapts. Participants will subsequently have weekly communication via phone call or email for support for the following 4 weeks, and upload their pump weekly. Investigators will log all time spent training and in communication with participant. Communication can be more often – as per clinical need, and logged. Visit 4D: Review of AHCL (after 4 weeks from commencement of AHCL, 1 hour) Face-to-face meeting to upload insulin pump, review CareLink reports and revise settings (CHO ratio and Insulin action time)

Participants will be issued with enough consumables for the study.

Visit 4 (participant randomised to control arm) (10 weeks after randomisation)

Visit 4A: First blinded sensor insertion

Visit 4B: Removal of blinded sensor and second blinded sensor insertion

VISIT 5 (12 weeks after randomisation; 1 hour)

The following data will be collected at the midpoint:

1 Auxological

Height, Weight, BMI, Blood pressure

- 2. Diabetes clinical
  - a. HbA1c
  - b. Total daily dose of insulin (mean of previous 7 days)
  - c. Pump upload (for both groups)
  - d. Sensor data in the 2 weeks prior to the study visit (in participants on CGM)
  - e. Clinical review
- 3. Psychological assessments
  - a. Functional health status: Quality of Life: EQ-5D-3L for 12 to ≤25yrs
  - b. Diabetes specific quality of life: PedsQL Child version (<13 yrs), Adolescent version (13 to <18 yrs) and young adult version (18 to ≤25 yrs)

  - c. Fear of hypoglycaemia: Hypoglycaemic Fear Survey-II Worry scale: 17 to ≤25yrs. Children's Hypoglycaemia Fear survey 12 to <17 yrs.
  - d. Impact and Satisfaction: Diabetes Technology Questionnaire, follow-up version (all ages: only for AHCL)
  - e. Diabetes distress: Problem Areas in Diabetes (Paediatric version 12 to <18 yrs, Standard version ≥18 yrs, Parent version)
  - f. Hypoglycaemia Awareness: Hypoglycaemia Awareness Scale (Gold Score) (all ages)

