4.8 Expected duration of the trial and participant participation, including a description of the sequence and duration of all techniques or assessments to be performed, including follow-up (e.g. interventions, procedures, measurements, observations, laboratory investigations). Provide a schedule of assessments in a table if possible.

The trial is expected to take 2.6 years for recruitment and completion of study visits. For each participant, the expected study duration is 13 months. The schedule of assessments is provided in the table below.

						Visits	5					
	Screen	1	2	3	4*	5	6	7	8	9*	10	11
					Primary ph	ase				Exten	sion phase: O	Optional
Length of time of visit (hours)		1- 2	0.5	4 - 6	6	1	0.5	0.5	2	6	1	2
Weeks from Randomisation (+/- 3 weeks window)		-2	-1	0	1 to 4	12	23	24	26	28	36	52
Informed Consent		X										
C-peptide	х											
HbA1c	х	х		х		х			х		х	х
Auxological data		х				х			х		х	х
Diabetes clinical data		х		x		х			x		х	x
bHCG		х										
Insulin pump upload		х		х		х			х		х	х
Carbohydrate Counting				x								
Diabetes education				х								
Blinded sensor		х	х		х		х	х				
Pump training					х					х		
CGM training					х					х		
AHCL commencement					х					х		
Pump/CGM data clinical review				x	x	х			х	x	х	
Psychology measures		х		х		х			x	х	х	x
Retinal Scan				х					х			х
Biomarkers				х					х			
Face-to-face Interview#									х			х
Phone Interview (optional)								х				
Medtronic Questionnaire (optional)				x				x				
		* AHCL: Visit # Random se	4 has 4 visits ( ection of part	4A,4B, 40	Cand 4D); Vis Perth will be	it 9 has 4 visit offered sem	ts( 9A,9B, 9C a i-structured in	and 9D); Cont nterview at st	rol: V4 at 10 udv end (V8	weeks after r or V11)	andomisatior	1

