# 4.9 Criteria for the termination of the trial. Description of the discontinuation criteria for individual participants, parts of the trial and entire trial.

Study participation is voluntary, and participants may withdraw at any time. The DSMB will report to the ethics committees and investigators if stopping the trial is required.

In general, once a participant is randomised, he/she will remain in the study unless the investigator believes it is not safe for the participant to continue. However, the criteria below will be used to determine whether use of the AHCL should be discontinued for a participant.

- 1. Severe hypoglycaemia (seizure or coma or any episodes requiring third party assistance).
- 2. Severe diabetic ketoacidosis (venous ph <7.2)
- 3. Participant pregnancy
- 4. Non-compliance with the protocol or development of a new medical condition or need for chronic use of a medication which in the judgment of the investigator increases risk for the participant

If AHCL use is stopped according to the above criteria, but the participant is willing, they will remain in the trial and will continue to make all of the scheduled visits and participate in all monitoring. The primary analysis will be intention to treat. Since participants in the usual care arm are following their normal diabetes care regimen, there will be no change in their participation in the trial if they experience one of the events that would trigger stopping.

Criteria for Suspending/Stopping Overall Study

The DSMB will have the responsibility of determining if the overall study should be stopped. In case of a recurring system malfunction or participant safety issue observed with multiple participants, the overall study will be suspended while the problem is diagnosed. The study may resume if the underlying problem can be corrected by a protocol or system modification that will not invalidate the results obtained prior to suspension.

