# 5.4 **Participant withdrawal criteria** (i.e. terminating investigational product/trial treatment) and procedures specifying:

(a) when and how to withdraw participants from the investigational product/trial treatment; The participant may withdraw from the study at any time. They can do so by contacting the research staff.

(b) the type and timing of the data to be collected for withdrawn participant(s); As this is an ITT, the data for withdrawn participants will be used for analysis

(c) whether and how participants are to be replaced; Participants will not be replaced.

(d) the follow-up for participants withdrawn from the investigational product/trial treatment. The participants will go back on their standard therapy and will be followed up as their regular clinic visits.

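### Section 9.5 replaces the promised intention-to-treat set with a one-visit rule that the two arms meet at different times, and 4.9 and 5.4(d) disagree on follow-up after AHCL is stopped

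*Protocol*

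**What the plan says.** **Analysis set.** Section 4.9 states: "The primary analysis will be intention to treat". Section 5.4(b) agrees: "As this is an ITT, the data for withdrawn participants will be used for analysis". Section 9.5, which defines the analysis populations, describes the primary approach as modified intention-to-treat, "with all randomised participants who attended at least one visit following randomisation being included in the analysis".

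**Timing of the first visit after randomisation.** Section 4.2 says of Visit 3: "This visit is the randomisation visit". The next visit in both arms is Visit 4. For AHCL it is a series of training and start-up visits (4A to 4D), which the section 4.8 schedule places in weeks 1 to 4. For controls, section 4.2 lists it as "Visit 4 (participant randomised to control arm) (10 weeks after randomisation"), and the footnote to the schedule repeats this. The schedule allows 3 weeks either side. Section 4.3 confirms that the trial is open label.

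**Follow-up after AHCL is stopped.** Section 4.9 says that if AHCL use is stopped under its criteria and the participant is willing, "they will remain in the trial and will continue to make all of the scheduled visits and participate in all monitoring". Section 5.4(d), under a heading about withdrawal from the investigational product or trial treatment, says: "The participants will go back on their standard therapy and will be followed up as their regular clinic visits".

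**Missing data.** Section 9.7 plans multiple imputation, with complete-case results also presented. Section 9.1 bases the comparison on baseline and Visit 8 (week 26).

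**The concern.** The protocol defines its primary set in two ways. A participant who withdraws before any visit after randomisation is in the analysis under 4.9 and 5.4(b), and out of it under 9.5.

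The rule in 9.5 also depends on arm. A modified intention-to-treat set is easiest to defend when allocation cannot influence who meets its condition. Here allocation is known, and the condition can be met within the first weeks on AHCL but not before about week 7 to 10 in the control arm. The same behaviour, leaving in week 6, leads to exclusion in one arm and to retention with an imputed outcome in the other. Section 6.3 describes a population whose adherence is already suboptimal, so early disengagement is foreseeable.

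The conflict between 4.9 and 5.4(d) affects the data themselves. Going back to standard therapy can only describe someone who was on AHCL, and 4.9 says that control participation does not change. A site that applied 5.4(d) to everyone who stops AHCL might not collect Visit 8 from them. That loss would fall in one arm, and no later analysis could recover it.

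**Working it through.** **The plan's own sample size.** The inputs in section 9.2 are a difference of 1.5, an SD of 1.7, alpha 0.05 (two-sided by section 9.3) and 80% power. The noncentral t gives 79.7% power at 21 per group and 81.6% at 22, so 22 per group is reproduced. Inflating 44 for 15% drop-out gives 44/0.85 = 51.8, or 52, against the stated 50. That figure is not at issue here.

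**Who the one-visit rule removes.** Inputs:
- 25 per arm (50 in two equal groups, section 9.2)
- drop-out d = 15% by week 26, which section 9.2 gives as an upper bound
- first visit at week 1 to week 4 for AHCL and week 10 for controls
- *assumption:* constant drop-out hazard, equal in both arms

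Fraction leaving before week w: f(w) = 1 − (1 − d)^(w/26).

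| First visit attended | f(w) at d = 15% | Expected excluded of 25 |
|---|---|---|
| AHCL, week 1 | 1 − 0.85^(1/26) = 0.62% | 0.16 |
| AHCL, week 4 | 1 − 0.85^(4/26) = 2.47% | 0.62 |
| Control, week 7 (earliest in window) | 1 − 0.85^(7/26) = 4.28% | 1.07 |
| Control, week 10 | 1 − 0.85^(10/26) = 6.06% | 1.51 |

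With the control visit at week 10, the gap is 1.51 − 0.62 = 0.9 to 1.51 − 0.16 = 1.4 patients (1.36 before rounding up). Controls are excluded roughly 2.5 to 10 times as often. With the control visit at week 7, the gap is 1.07 − 0.62 = 0.45 to 1.07 − 0.16 = 0.9. A linear spread of drop-out hardly changes this: 0.15 × 10/26 = 5.8%, or 1.4 of 25 controls.

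Over an assumed drop-out range of 5% to 25%, 0.5 to 2.6 controls are excluded and the gap is 0.3 to 2.3 patients. If all 15% of control drop-out came before week 10, 0.15 × 25 = 3.75 controls would be excluded.

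**What that could do to an arm mean.** If excluded participants differ from retained ones by D, excluding a fraction f shifts that arm's mean by f × D. Take D = 1.7, a full SD (assumption). The net shift between arms is then (6.06% − 2.47%) × 1.7 = 0.06 to (6.06% − 0.62%) × 1.7 = 0.09 HbA1c points, against a planned 1.5. With all control drop-out early, the control mean shifts by 0.15 × 1.7 = 0.26. The sign of D is unknown.

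**What changing the set would recover.** A control who leaves before week 10 has neither the Visit 5 HbA1c (week 12) nor the Visit 8 outcome. Imputation that assumes data missing at random would fill in such a person from baseline and from the retained controls, so the control mean would hardly move. In the complete-case analysis the person is absent under either set.

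**Follow-up passages side by side.** Section 4.9 covers AHCL stopped under its listed criteria and keeps the willing participant at every visit. Section 5.4(d) is headed for withdrawal from trial treatment and names only routine clinic follow-up. A participant who stops AHCL but is willing to stay fits both descriptions, and the two give different follow-up.

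**The case against.** Section 9.5 is the dedicated section on analysis populations and is explicit. Sections 4.9 and 5.4(b) mention intention to treat while making the point that people who stop or withdraw are still analysed, and 9.5 also includes them once they have attended one visit. Section 9.4 requires deviations from the statistical plan to be reported. A reader might infer that the analysis set could be picked freely once the data are seen, and these sections do not support that. The contradiction still needs removing.

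A reader might also infer that the rule removes only controls, or that it biases the result in a known direction. Neither follows. AHCL participants who leave before Visit 4A are excluded too, the expected gap is about one patient at a drop-out rate the plan gives as its maximum, and the documents do not say how early leavers would have fared. Nor would changing the set recover the shifts calculated above, because the outcomes of those early leavers are unobserved either way. These objections stand, and they limit the size of the point.

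A third tempting reading is that 5.4(d) ends study follow-up for everyone who stops AHCL. Section 4.9 says otherwise for willing participants. The answer at 5.4(a) speaks of leaving the study, so 5.4(d) may be meant only for people who leave altogether. Its heading, about withdrawal from trial treatment, leaves that open. What can be said is that the two sections conflict as worded.

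**Conclusion.** The point holds in limited form. The protocol contradicts itself on the primary set, and the rule in 9.5 treats identical early drop-out differently by arm in an open-label trial. The expected imbalance is about 1.5 of 25 controls against 0.2 to 0.6 of 25 AHCL participants. This assumes 15% drop-out, a constant hazard equal in both arms, and visits at their nominal weeks. The effect on the estimate is probably small, and its direction cannot be stated.

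The conflict between 4.9 and 5.4(d) has no number attached, because it depends on how sites read it. Its worst case is missing Visit 8 data in the AHCL arm only. Both matters should be corrected; neither by itself invalidates the trial.

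**What to change.** - In 9.5, define the primary set as all randomised participants, analysed in the arm to which they were allocated, with the multiple imputation already planned in 9.7. Keep the one-visit set as a sensitivity analysis.
- Use the same definition in 4.9 and 5.4(b).
- Reconcile 5.4(d) with 4.9 by separating stopping AHCL from withdrawing consent. Anyone who stops AHCL but has not withdrawn consent should still be asked to attend the scheduled outcome visits, including Visit 8. This concerns data collection only, not when AHCL is stopped or what treatment follows.

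The cost is a small protocol wording change. Imputation adds little for people with baseline data only, so the main gain is a set that does not depend on arm and a Visit 8 outcome sought from both arms alike.

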4.2 Type (e.g. phase, pilot) and design (e.g. double-blind, placebo-controlled, parallel design) of the trial to be conducted and a schematic diagram of the trial design, procedures and stages (e.g. initial assessment, run-in, pre-randomisation assessment, randomisation, treatment phase, end-of-treatment assessment, washout, cross-over, alternative treatment, post-treatment assessments, trial exit).

This is a **prospective multicentre randomised controlled, two-arm unblinded, parallel study** in free-living conditions, in adolescents with type 1 diabetes on insulin pump therapy. Participants are randomized in two groups; either the control group (standard therapy) or the intervention group (advanced hybrid closed loop). The control group will be participants on insulin pump therapy with or without CGM (continuous glucose monitoring).

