# AHCL arm: Medtronic MiniMed™ 670G 4.0 / 780G for 6 months OR

#### Conventional arm: Standard care for 6 months. This will be followed by an optional extension phase for another 6 months.

The study will be conducted at four tertiary paediatric diabetes centres (Perth Children's Hospital, WA, Westmead Children's Hospital, NSW, Women's and Children's Hospital, SA, and Royal Children's Hospital, VIC). A home visit may be offered for some visits which involve insertion or return of blinded sensors prior to randomisation, mid and end of the study. This provides a patient centric approach working within the parameters of local policies and procedures on home visits.

**Pre-screening**: HbA1c, and fasting C-peptide for eligibility will be required, to occur within 3 months of formal screening.

All participants on CGM are encouraged to wear their sensor in the weeks preceding Visit 1.

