  - g. Generalized Anxiety Disorder-7 and Patient Health Questionnaire-9 (12 to 25 years)
  - h. Physical activity: The Active Australia Survey (all ages)
  - i. INSPIRE questionnaire (follow-up assessment for those on AHCL)

Participants in the intervention group will be issued with enough consumables for the study

**VISIT 6** (23 weeks after randomisation; 30 mins)

Insertion of first blinded CGM (4th generation sensor and transmitter) to collect end-of -study glycaemic data. This constitutes first of the two sensors, each sensor provides data for 7 days. Participants will be instructed to test minimum 4x/day using CONTOUR® NEXT LINK 2.4 glucometer.

VISIT 7 (24 weeks after randomisation; 30 mins)

Insertion of second blinded CGM Participants will return 7 days after sensor insertion to download the first week of CGM data. The CONTOUR® NEXT LINK 2.4 glucometer will be uploaded. A new sensor will be inserted and a fresh transmitter attached.

Medtronic AHCL System Post-Study Patient Questionnaire (Optional) Phone interview (Optional)

**VISIT 8** (26 weeks after randomisation; 2 hours)

The following data will be collected.

1. Auxological

Height, Weight, BMI, Blood pressure

- 2. Diabetes clinical
  - a. HbA1c

- b. Total daily dose of insulin (mean of previous 7 days)
- c. Carbohydrate ratios and insulin sensitivity factors
- d. Pump upload (for both groups)
- e. CGM data from second blinded CGM
- f. Sensor data in the 2 weeks prior to the study visit (in participants on CGM)
- g. Clinical review
- 3. Psychological assessments
  - 1. Functional health status: Quality of Life: EQ-5D-3L for 12 to ≤25yrs
  - 2. Diabetes specific quality of life: PedsQL Child version (<13 yrs), Adolescent version (13 to<18yrs) and young adult version (18 to ≤25 yrs)
  - 3. Fear of hypoglycaemia: Hypoglycaemic Fear Survey-II Worry scale: 17 to ≤25yrs. Children's Hypoglycaemia Fear survey 12 to <17 yrs.
  - 4. Impact and Satisfaction: Diabetes Technology Questionnaire: Follow-up version (all ages only for AHCL)
  - 5. Diabetes distress: Problem Areas in Diabetes (Paediatric version 12 to <18 yrs, Standard version ≥18yrs, Parent version)
  - 6. Hypoglycaemia Awareness: Hypoglycaemia Awareness Scale (Gold Score) (all ages)
  - 7. Generalized Anxiety Disorder-7 and Patient Health Questionnaire-9 (12 to 25 years)
  - 8. Physical activity: The Active Australia Survey (all ages)
  - 9. INSPIRE questionnaire (follow-up assessment for those on AHCL)

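### The per-protocol rule on pump and sensor adherence is not split by arm and, read as written, excludes compliant controls who do not use CGM

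*Protocol*

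**What the plan says.** Section 9.5 makes the primary analysis modified intention-to-treat and then adds "A secondary analysis using a 'per-protocol' sample", "defined as participants with over 70% adherence to pump and sensor". There is no version of the rule for each arm. The sentence does not say which sensor is meant or over what period adherence is measured.

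Section 4.2 describes the comparator: "The control group will be participants on insulin pump therapy with or without CGM". The arm is labelled "Conventional arm: Standard care for 6 months", and no CGM for treatment is issued to it during those six months. The visit lists in section 4.2 collect personal CGM data only from those who have it: "Sensor data in the 2 weeks prior to the study visit (in participants on CGM").

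Controls do wear blinded sensors. Two are scheduled from about week 10 ("Visit 4B: Removal of blinded sensor and second blinded sensor insertion") and two more from week 23. For the week-23 collection the protocol says: "This constitutes first of the two sensors, each sensor provides data for 7 days".

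**The concern.** A per-protocol set should hold the people who followed what their arm required. In the AHCL arm, wearing pump and sensor is the assigned treatment. In the control arm, wearing a sensor is a feature of some people's usual care and is not required. A single pump-and-sensor threshold therefore measures compliance in one arm and type of usual care in the other.

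Taken literally, a control on a pump without CGM can follow the protocol completely and still be left out. The controls who remain are those who already wear CGM most of the time. The contrast then sets adherent AHCL users against CGM-wearing pump users, which is not the standard-care comparator that was randomised. The minimisation in section 4.3 uses age, HbA1c and site, not CGM use, so it does nothing to keep these subsets comparable.

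Two things are at stake: the meaning of the per-protocol contrast, and its precision in a trial of only 50 participants.

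**Working it through.** **Step 1: can a control without CGM meet the rule?** Inputs from section 4.2: two blinded sensors from about week 10, two from week 23, final visit at week 26. Seven days per sensor is stated for the week-23 collection and is assumed here for the week-10 pair.

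- Treatment period: 26 × 7 = 182 days.
- Scheduled sensor wear after randomisation: 4 × 7 = 28 days.
- Share: 28/182 = 15.4%. If only the end-of-study pair counts, 14/182 = 7.7%.

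Both are far below 70%. The baseline blinded sensors come before randomisation and do not help. Section 4.2 has another 70% rule, at Visit 2, but that governs whether the run-in data suffice and is not tied to the per-protocol set.

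**Step 2: are such controls expected?** The inclusion criteria in section 5.2 require pump therapy but not CGM. Section 5.3 excludes only those who started CGM in the 3 months before screening. Visit 4B provides for participants new to sensors. The protocol clearly expects some, but gives no proportion.

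**Step 3: the plan's own sample size.** Inputs from sections 9.2 and 9.3: difference 1.5%, SD 1.7%, two-sided alpha 0.05, power 80%, equal groups, dropout up to 15%.

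- Normal approximation: n = 2 × (1.96 + 0.84)² × (1.7/1.5)², which rounds up to 21 per group.
- Two-sample t-test: 21.17, so 22 per group, as stated. Power at 22 per group is 81.6%.
- Dropout: 44/0.85 gives 52 against 50 planned. This small gap does not matter here. Working back, 50 × 0.85/2 = 21.25, about 21 evaluable per arm.

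**Step 4: precision of the per-protocol contrast.** Let *f* be the share of the 21 evaluable controls who qualify. This is an assumption, since the protocol gives no figure. Take all 21 AHCL participants as adherent. Relative to 21 per arm, the standard error grows by √[(1/21 + 1/(21*f*))/(2/21)] = √[(1 + 1/*f*)/2]. Power is from the two-sample t-test with the planning difference and SD.

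| Share of controls qualifying | Controls left | SE ratio | Power, all AHCL adherent | Power, 70% of AHCL adherent |
|---|---|---|---|---|
| 100% | 21 | 1.00 | 80% | 71% |
| 75% | 15.75 | √1.167 = 1.08 | 73% | 65% |
| 50% | 10.5 | √1.5 = 1.22 | 62% | 55% |
| 25% | 5.25 | √2.5 = 1.58 | 41% | 38% |

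The SE ratio is for the case where all AHCL users are adherent. In the last column, 70% is an illustrative share of people who pass the rule. It is not the wear threshold, and nothing in the protocol supports that share over another.

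**Step 5: direction of bias.** Keeping only CGM-wearing controls could favour the control side if they have better glycaemic control. Keeping only adherent AHCL users could favour the AHCL side if they are more motivated. The documents give no basis for saying which would dominate.

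**The case against.** The strongest reply is that the sentence is brief and can be read in ways that avoid the problem. Adherence presupposes something assigned, and a control without CGM was assigned no personal sensor. The rule might be meant for the AHCL device pair only. It might instead mean compliance with the blinded sensors scheduled for everyone, which a control without CGM could meet. Detailed definitions of sensor, window and arm are often left to a statistical analysis plan, and that plan is not shown.

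Part of this stands. A reader might infer that every control without CGM has zero adherence and can never qualify. The protocol does not say that, because it names neither the sensor nor the period. It also states neither of the milder readings. What it does state is one rule for all participants, and that rule does not fit its own description of the control arm.

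Other stronger readings also go beyond the documents:

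- **That the trial's main conclusion is at risk.** The set serves a secondary analysis only.
- **That the trial's adherence question rests on this contrast.** Sections 1.2 and 2.1 ask whether managing AHCL is less of a challenge than routine treatment. Section 4.1 takes adherence patterns up under human factors, and the interviews also address them.
- **That a small or reversed per-protocol effect would be an artefact.** It could be one, but it could also be real or due to chance.
- **That most of the control arm will be lost.** This depends on an unknown CGM share. If 75% of controls qualify, only a quarter are lost.

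**Conclusion.** The point holds as a defect in a stated definition. Read as written over the six-month treatment period, section 9.5 excludes controls who complied fully but do not use CGM, and it leaves frequent CGM wearers as the only comparators. Bias could run either way.

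The loss of precision ranges from small to severe: about 73%, 62% or 41% power for the 1.5% HbA1c difference if 75%, 50% or 25% of controls qualify, against about 80% if all do. These figures rest on 21 evaluable per arm, full AHCL adherence, the planning SD of 1.7% and an unadjusted t-test. They also take the true difference to be unchanged in the selected subset, which need not be so. The qualifying share is assumed throughout.

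The modified intention-to-treat primary analysis is not affected. This should be corrected before the data are examined, because choosing the set afterwards would be post hoc.

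**What to change.** Replace the single rule with a definition for each arm:

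- **AHCL arm:** over 70% use of the study pump and study sensor, naming the sensor, the measure of use and the period over which it is counted.
- **Control arm:** remained on pump-based standard care and did not use closed loop, with no condition on sensor wear.

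The change is a sentence or two and needs no new data, since pump uploads are already planned for both groups at the follow-up visits.

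The remaining limit should be stated with it. Selection on adherence persists in the AHCL arm while controls are hardly selected, so the two subsets are still not exchangeable and the result is supportive only.

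A complier-average estimate, with randomised arm as the instrument, would keep everyone randomised. It is at most an optional supplement. With a 70% cut-off it assumes that AHCL use below 70% has no effect, which is doubtful for a device in continuous use, and that assumption would have to be stated. Its interval would also be wider than that of a naive per-protocol comparison.
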